7.5.2.1.2 Time to death

A stratified log-rank test will be used to evaluate the effect of Nintedanib on time to death compared to Placebo. The test will be stratified by the randomisation stratification variable HRCT pattern ("HRCT with UIP-like fibrotic pattern only" vs. "Other HRCT fibrotic patterns", as documented in the CRF). A Cox proportional-hazards model stratified by the same factors as the log-rank test will be used to derive the hazard ratio and 95 % confidence interval (CI) between the two randomised treatment regimens (Hazard ratios <1 will favour nintedanib). In the co-primary population of patients with "HRCT with UIP-like fibrotic pattern only", the respective analyses will be performed without stratification.

Breslow's method for handling ties will be used. Kaplan-Meier plots by treatment group will also be presented. The assumption of proportional hazards and the homogeneity of the hazard ratio will be checked descriptively.

If the proportion of patients experiencing an event is less than 5%, only frequencies of events by treatment group will be provided for this endpoint. In this case no other analyses will be performed.

7.5.2.1.3 Time to first acute ILD exacerbation or death

The same type of evaluation as described for time to death (see [Section 7.5.2.1.2](#)) will be implemented. If, however, the proportion of patients experiencing at least 1 acute ILD exacerbation over 52 weeks is less than 5%, then only frequencies of events by treatment group will be provided for this endpoint. In this case no other analyses will be performed.

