In trial 1199.34, the frequency of patients with at least 1 acute IPF exacerbation over 52 weeks based on Investigator reporting was lower in the nintedanib group (3.6%) than in the placebo group (9.6%). The hazard ratio (HR) of 0.38 (95% CI 0.19, 0.77) indicated a significantly lower risk of having a first acute IPF exacerbation in the nintedanib group than in the placebo group at any time point over 52 weeks. In trial 1199.32, the frequency of patients with at least 1 acute IPF exacerbation based on Investigator reported adverse events was 6.1% in the nintedanib group and 5.4% in the placebo group; the HR was 1.15 (95% CI 0.54, 2.42), indicating no significant difference in the risk of first acute IPF exacerbation between the treatment groups. In the phase II trial 1199.30, the number of patients with acute IPF exacerbations over 52 weeks was lower in the nintedanib group (2.3%) compared to placebo (13.8%). The estimated HR of nintedanib versus placebo was 0.16 (95% CI 0.04,

0.71; $p=0.0054$) indicating a significantly lower risk of having an acute IPF exacerbation in the nintedanib group than in the placebo group.

In the pre-specified pooled analysis of the Phase III studies 1199.32 and 1199.34, consistent with the effect of nintedanib on the decline in lung function, overall mortality over 52 weeks was numerically lower in the nintedanib group (5.5%) than in the placebo group (7.8%). The analysis of the time to death resulted in a hazard ratio (HR) of 0.70 (95% CI 0.43, 1.12; $p=0.1399$) indicating a 30% reduction in the risk of death in the nintedanib group compared with placebo. The results of all survival endpoints (such as on-treatment mortality and respiratory mortality) showed a consistent numerical difference in favour of nintedanib.

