7.3.2 Secondary endpoint analyses

Secondary endpoints are defined in [Section 5.1.2](#).

For all secondary endpoints, an intent-to-treat principle will be used (i.e. all available data from the treated set within the first 52 weeks will be used, including data for patients who prematurely discontinued randomized treatment).

Continuous endpoints will be analysed using a restricted maximum likelihood (REML) based repeated measures approach. Analyses will include the fixed, categorical effects of HRCT pattern (except for the analyses on the co-primary analysis population assessing only patients with HRCT with UIP-like fibrotic pattern only), treatment, visit, and treatment-by-visit interaction, as well as the continuous, fixed covariates of baseline and baseline-by-visit interaction. An unstructured (co)variance structure will be used to model the within-patient measurements.

If this analysis fails to converge, the following covariance structures will be tested in order: heterogeneous toeplitz (TOEPH), toeplitz (TOEP) and autoregressive 1 (AR[1]). The first model to converge will be used. The Kenward-Roger approximation will be used to estimate denominator degrees of freedom. Significance tests will be based on least-squares means using a two-sided $\alpha = 0.05$ (two-sided 95% confidence intervals). In case the model fails to converge under PROC MIXED, the “singular” option will be considered. The treatment comparisons will be the contrast between treatments at week 52.

Time-to-event endpoints will be analysed using a Cox proportional hazards model. The equality of the hazard rates will be tested by the Wald test for the treatment effect at the two-sided 5% significance level. The model will include the treatment effect and HRCT pattern (except for the analyses on the co-primary analysis population assessing only patients with HRCT with UIP-like fibrotic pattern only) as covariates. Breslow’s method for handling ties will be used. Kaplan-Meier plots by treatment group will also be presented. If the proportion of patients experiencing at least 1 acute ILD exacerbation over 52 weeks is less than 2%, then only frequencies of exacerbations by treatment group will be provided for the main secondary endpoint of time to first acute ILD exacerbation or death over 52 weeks and no statistical analysis will be performed.

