4.2 CHANGES

The following changes compared to the plans outlined in the CTP will be implemented:

- In Section 7.3.2 (Secondary endpoint analyses) of the CTP it is written that convergence issues observed in the analysis of continuous endpoints via a restricted maximum likelihood (REML) based repeated measures approach would be tackled by applying different covariance structures. The exact wording is: "If this analysis fails to converge, the following covariance structures will be tested in order: heterogeneous toeplitz (TOEPH), toeplitz (TOEP) and autoregressive 1 (AR[1]). The first model to converge will be used." It is not intuitive why a different approach should be used for a secondary or further endpoint compared to what is done when the primary analysis shows similar issues. Hence, the analysis approach for convergence issues for continuous secondary or further endpoints will be modified to follow the one used for the primary analysis.
- In Section 7.3.2 (Secondary endpoint analyses) of the CTP it is written that Time-to-event (TTE) endpoints will be analysed using a Cox proportional hazards model. The exact wording is: "Time-to-event endpoints will be analysed using a Cox proportional hazards model. The equality of the hazard rates will be tested by the Wald test for the treatment effect at the two-sided 5% significance level. The model will include the treatment effect and HRCT pattern (except for the analyses on the co-primary analysis population assessing only patients with HRCT with UIP-like fibrotic pattern only) as covariates. Breslow's method for handling ties will be used. Kaplan-Meier plots by treatment group will also be presented. If the proportion of patients experiencing at least 1 acute ILD exacerbation over 52 weeks is less than 2%, then only frequencies of exacerbations by treatment group will be provided for the main secondary endpoint of time to first acute ILD exacerbation or death over 52 weeks and no statistical analysis will be performed." While the Cox Model is still employed to compute the effect size, i.e. the hazard ratio, a stratified log-rank test will be used to evaluate the effect of nintedanib on TTE endpoints compared to placebo.

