5.2.2.1.3 Time to first acute ILD exacerbation or death over 52 weeks

Acute ILD exacerbation is defined in the CTP as an acute, clinically significant, respiratory deterioration characterized by evidence of new widespread alveolar abnormality with all of the following:

- Previous or concurrent diagnosis of ILD
- Acute worsening or development of dyspnoea typically less than one month duration
- Computed tomography with new bilateral ground-glass opacity and/or consolidation superimposed on a background pattern consistent with fibrosing ILD
- Deterioration not fully explained by cardiac failure or fluid overload

Events that are clinically considered to meet the definition of acute exacerbation but fail to meet all four diagnostic criteria due to missing CT data should be termed “suspected acute exacerbations”. Please note that only acute ILD exacerbations that fulfil all the criteria depicted above will be taken into account and contribute to the endpoint. Information on acute ILD exacerbations will be obtained from the Adverse Events page.

For those patients who either experience acute ILD exacerbations or who die due to any cause within the first 52 weeks, time to first acute ILD exacerbation or death [days] will be computed as:

- Earliest of date of first documented acute ILD exacerbation or death – date of first drug intake + 1

Patients who did not experience any ILD exacerbation event within the first 52 weeks will be censored according to the mechanism for censoring as described in [Table 5.2.2.1.3: 1](#).

Table 5.2.2.1.3: 1 Censoring Rules for Time to first acute ILD exacerbation or death over 52 weeks

Rule #	Situation	Outcome (event or censored)	Date of event or censoring
1	Patient had a documented acute ILD exacerbation or died within the first 52 weeks and the date of the event is known	Event	Earliest Date of event
2	Patient had a documented acute ILD exacerbation or died within the first 52 weeks and the date of the event is unknown	Event	Imputed date of event
3	Patient did not have a documented acute ILD exacerbation and is alive after 52 weeks	Censored	Day 373 (372 days after first drug intake)
4	Patient status is unknown	Censored	Date of last contact when the patient was known to be alive and event free

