7.5.2.2.2 Time to progression or death

The same type of evaluation as described for time to death (see [Section 7.5.2.1.2](#)) will be implemented for this endpoint. If, however, the proportion of patients experiencing a progression (see [Section 5.2.2.2.2](#) for details about the definition of progression) within the 52 week period is less than 5%, then only frequencies of events by treatment group will be provided. In this case no other analyses will be performed.

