7.6.1 Over 52 weeks

7.6.1.1 Time to first non-elective hospitalisation or death

The same type of evaluation as described in [Section 7.5.2.1.2](#) will be implemented. If, however, the proportion of patients experiencing a non-elective hospitalisation over 52 weeks is less than 5%, then only frequencies of events by treatment group will be provided for this endpoint. In this case no other analyses will be performed.

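### The SAP raises the cut-off for analysing exacerbation or death from 2% to 5% without declaring it, and still counts exacerbations only

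*SAP*

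**What the plan says.** Protocol 7.3.2 has one event-rate rule for time-to-event endpoints, and it applies only to time to first acute ILD exacerbation or death. If "the proportion of patients experiencing at least 1 acute ILD exacerbation over 52 weeks is less than 2" per cent, frequencies are given and no statistical analysis is done. Time to death has no such rule.

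SAP 7.5.2.1.3 applies the rule to the same endpoint if "the proportion of patients experiencing at least 1 acute ILD exacerbation over 52 weeks is less than 5" per cent. SAP 7.5.2.1.2 adds a rule for time to death: "If the proportion of patients experiencing an event is less than 5" per cent, only frequencies are shown. In both cases all other analyses are dropped, which removes the log-rank test, hazard ratio, confidence interval and Kaplan-Meier plot.

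SAP 4.2 is the list of changes from the protocol. It reproduces the protocol paragraph, including the 2% figure, and then announces one change: "a stratified log-rank test will be used to evaluate the effect of nintedanib on TTE endpoints compared to placebo". SAP 4.1, SAP 4.3 and the history table mention neither cut-off.

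The composite's event time is derived "For those patients who either experience acute ILD exacerbations or who die due to any cause within the first 52 weeks" (SAP 5.2.2.1.3), so every death is an event. Only exacerbations meeting all four criteria count; suspected ones do not.

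Two other composites have the same feature. Progression or death depends on "the proportion of patients experiencing a progression" (SAP 7.5.2.2.2). Hospitalisation or death is dropped if "the proportion of patients experiencing a non-elective hospitalisation over 52 weeks is less than 5" per cent (SAP 7.6.1.1). The whole-trial versions (SAP 7.6.2.1, 7.6.2.4, 7.6.2.5) repeat it. Respiratory death also has a 5% rule that the protocol lacks (SAP 7.5.2.2.1).

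**The concern.** There are two faults.

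The first is traceability. Two of the three main secondary endpoints can be reduced to counts under rules that differ from the protocol. A reader of SAP 4.2 would conclude that 2% still applies.

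The second is the basis of the count. The composite contains every death, so it never has fewer events than time to death. Yet its cut-off ignores deaths, while time to death is judged on its own events. Sparse data cannot justify dropping the endpoint with more events and keeping its component. The protocol already counts exacerbations only, but at 2% this hardly mattered. At 5% it can.

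SAP 7.5.2.1.3 also does not say whether the proportion is pooled over arms, or whether it is judged once or separately in each co-primary population.

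At stake is the effect estimate for an endpoint that Protocol 7.7 counts among the main support for the primary result.

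**Working it through.** The plan gives no operating characteristics for these cut-offs, so it has no figure of its own to reproduce.

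**Inputs**
- Sample size: 600 overall and 400 UIP-like, 1:1 (Protocol 7.7).
- IPF exacerbation rates (Protocol 1.2), averaged 1:1 over nintedanib and placebo. In trial 1199.32 the proportion "was 6.1% in the nintedanib group and 5.4% in the placebo group", average (6.1 + 5.4)/2 = 5.75%. Trial 1199.34: (3.6 + 9.6)/2 = 6.6%. Trial 1199.30: (2.3 + 13.8)/2 = 8.05%. Mean of the two Phase III trials: (5.75 + 6.6)/2 = 6.175%.
- Mortality: (5.5 + 7.8)/2 = 6.65% from the pooled Phase III IPF trials (Protocol 1.2). Protocol 7.7 expects PF-ILD mortality to be similar to IPF.
- The PF-ILD exacerbation rate is not given. Rates of 4% and 5% are assumed to show the range.

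**Step 1: where the rules bite.** 2% of 600 is 12 and 5% is 30. The protocol drops the analysis at 11 or fewer patients with an exacerbation, the SAP at 29 or fewer. For 400 patients the limits are 7 and 19.

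**Step 2: chance that the 5% rule fires.** P(X ≤ 29) with X ~ Bin(600, p), and P(X ≤ 19) with X ~ Bin(400, p), pooled over arms:

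| Exacerbation rate | n = 600 | n = 400 |
|---|---|---|
| 4% (assumed) | 87% | 82% |
| 5% (assumed) | 47% | 47% |
| 5.75% (1199.32) | 19% | 23% |
| 6.175% (Phase III mean) | 10% | 14% |
| 6.6% (1199.34) | 4% | 8% |
| 8.05% (1199.30) | 0.1% | 0.7% |

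Under the 2% rule the chance is largest at 4%, where it is 0.2% (n = 600) and 0.9% (n = 400).

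**Step 3: the mismatch.** Take 29 patients with an exacerbation and 0.0665 × 600 = 39.9, about 40 deaths. Time to death is analysed, because 40 is above 30. The composite has between 40 patients with an event (every patient with an exacerbation also dies) and 40 + 29 = 69 (no overlap). It gets frequencies only.

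At 6.65% mortality the chance that deaths reach 5% is 0.96 (n = 600) or 0.93 (n = 400). If exacerbation and death counts were independent, the chance of dropping the composite while analysing death would be 0.18 or 0.21 at a 5.75% exacerbation rate.

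**Step 4: what is lost.** The 95% CI factor either way is exp(1.96 × 2/√d), which is 1.86 at d = 40 events and 1.60 at d = 69. Power at HR 0.70, two-sided 5%, is Φ(√d/2 × |ln 0.70| − 1.96):
- d = 40: Φ(1.128 − 1.96) = 20%
- d = 69: Φ(1.481 − 1.96) = 32%

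**Step 5: judging each population separately.** Let X1 ~ Bin(400, p) and X2 ~ Bin(200, p), with equal rates in both strata assumed. The chance that exactly one of X1 < 20 and X1 + X2 < 30 holds is 19% at 5%, 14% at 5.75% and 6% at 6.6%.

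**Step 6: a cut-off on the composite's own events.** The least favourable case is full overlap, where composite events equal deaths: P(Bin(600, 0.0665) ≤ 29) = 0.039. The rule would then fire in at most 4% of trials.

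**The case against.** Counting exacerbations only comes from the protocol, which has no cut-off for death, so the mismatch was already possible. It also has a rationale: with few exacerbations the composite is mostly time to death, which keeps its own estimate. Changing the basis would itself depart from the protocol. The large probabilities use assumed rates; at the IPF trial rates they are 19%, 4% and 0.1%. Secondary p-values are nominal, the trial is powered only for the primary endpoint, and the lost hazard ratio would be imprecise. Event frequencies remain, and SAP 7.8.1.4 provides Kaplan-Meier plots of time to first ILD adverse event with no 5% condition stated there. Where the SAP means per arm it usually says so, so an unqualified proportion reads as pooled.

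Much of this stands and limits the seriousness. It does not remove the two faults. A departure from the protocol can be made if it is declared, and these were not. The higher cut-off turns a remote mismatch into a realistic one. The SAP 7.8.1.4 plots use on-treatment censoring and leave out death, and that section does not say that ILD there means acute exacerbation, so they are only a partial substitute. The IPF Phase III rates were investigator-reported, while the SAP leaves out suspected exacerbations. If that lowers the counted rate, the rule fires more often. Pooled is the natural reading, but whether the decision is made once or per population is still open.

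**Conclusion.** The concern holds. The SAP changes the cut-off for one main secondary endpoint from 2% to 5% and adds one to another, and its list of changes mentions neither. As written, the rule can leave a composite of 40 to 69 events with counts only while time to death, with 40 events, is analysed.

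How likely this is depends on the PF-ILD exacerbation rate, which the documents do not give. For the overall population the rule fires in 0.1% to 19% of trials at the three IPF trial rates, and in about half or more if the rate is 5% or lower. These figures assume a proportion pooled over arms and 600 patients.

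The loss would be an estimate and a plot, not a decisive test. The primary analysis and its type I error are not affected. The SAP should be corrected, but the trial's main conclusion does not turn on it.

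**What to change.** 1. In SAP 7.5.2.1.3, count patients with an exacerbation or death towards the cut-off, as SAP 7.5.2.1.2 already does for its own events. Do the same in SAP 7.5.2.2.2, 7.6.1.1, 7.6.2.1, 7.6.2.4 and 7.6.2.5. At the least, restore the protocol's 2% for the exacerbation composite.
2. State that the proportion is pooled over arms and that one decision, taken on the overall population, applies to both co-primary populations.
3. List and justify in SAP 4.2 every cut-off that departs from the protocol, including those for time to death and respiratory death and, if adopted, the new counting basis.

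This is SAP wording only, to be settled before unblinding. The cost is that a hazard ratio with a wide interval may be reported when events are few: at 30 events the factor is exp(1.96 × 2/√30) = 2.05 either way. With few exacerbations the composite will also largely repeat time to death.

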7.5.2.2 Other secondary efficacy endpoints

7.5.2.2.1 Time to death due to respiratory cause

In general, the same type of evaluation for time to death due to respiratory cause will be implemented as described for time to death (see [Section 7.5.2.1.2](#)). However; only patients whose cause of death was attributed to respiratory causes (as determined by an independent adjudication committee) will be included. If the proportion of such patients within the first 52 weeks is less than 5%, then only frequencies of events by treatment group will be provided for this endpoint. In this case no other analyses will be performed.

7.5.2.2.2 Time to progression or death

The same type of evaluation as described for time to death (see [Section 7.5.2.1.2](#)) will be implemented for this endpoint. If, however, the proportion of patients experiencing a progression (see [Section 5.2.2.2.2](#) for details about the definition of progression) within the 52 week period is less than 5%, then only frequencies of events by treatment group will be provided. In this case no other analyses will be performed.

7.5.2.2.3 Relative decline from baseline in FVC % pred

Patients will be categorised based on the relative decline since baseline in FVC % pred greater than 5% or 10%. Comparisons between treatment groups will be performed using a logistic regression model adjusting for the continuous covariate baseline FVC % pred and the binary covariate HRCT pattern. The likelihood-ratio test will be used to test for differences between treatments. Adjusted odds ratios together with 95% confidence intervals will be used to quantify the effect of treatment, comparing nintedanib 150 mg bid to placebo as the reference. Additionally, descriptive analyses of the relative change from baseline in FVC % pred will be shown, for the co-primary populations as well as for the complementary population.

7.5.2.2.4 Living with Pulmonary Fibrosis Symptoms and Impact Questionnaire (L-PF)

The absolute change from baseline in L-PF symptoms dyspnoea domain score between week 52 and baseline will be presented graphically as well as numerically to illustrate the impact of the underlying condition on the patient's health status.

The absolute change from baseline in L-PF symptoms cough domain score between week 52 and baseline will be presented graphically as well as numerically to illustrate the impact of the underlying condition on the patient's health status.

The descriptive analyses of the absolute change from baseline in L-PF symptoms dyspnoea domain score as well as L-PF symptoms cough domain score will also be shown for the complementary population.

In addition to the descriptive evaluation, absolute change from baseline in L-PF symptoms dyspnoea domain score between week 52 and baseline, as well as in L-PF symptoms cough domain score between week 52 and baseline will also be analysed using a restricted maximum likelihood (REML) based repeated measures approach. An unstructured variance-covariance structure will be used to model the within patient measurements. In the event of non-convergence, the same methods used in the primary analyses ([Section 7.4.1](#)) will be implemented to overcome the issue. The HRCT pattern will be included as a covariate (with exception when the analysis is run in the co primary population of patients with "HRCT with UIP-like fibrotic pattern only") as well as the respective baseline L-PF symptoms score.

7.6 FURTHER ENDPOINTS

All further endpoints will be considered exploratory in nature, and no p-values will be presented.

7.6.1 Over 52 weeks

7.6.1.1 Time to first non-elective hospitalisation or death

The same type of evaluation as described in [Section 7.5.2.1.2](#) will be implemented. If, however, the proportion of patients experiencing a non-elective hospitalisation over 52 weeks is less than 5%, then only frequencies of events by treatment group will be provided for this endpoint. In this case no other analyses will be performed.

